13.3 Methods for Resistance Testing

13.3.1 Isolation & Identification of Organisms Using Microbiological Techniques

Various organisms from nasal, nasopharyngeal, and rectal swabs will be isolated using the media and conditions in Table 2 and identified using the methods summarized in Table 3 and below. Standard microbiological handbooks should be referenced for more detailed information.

Procedure for Masking Samples

The microbiologist and all lab staff will be masked to the community of origin.

Laboratory Results Reporting

All lab results will be kept in computer files as well as in hard-copy form by the Microbiologist.

Table 2. Isolation of Organisms from Source - Primary Plating Media & Incubating Conditions

Source	Media	Incubation	Organisms Isolated
Nasal Swab	Blood and MSA	35°C 5% CO ₂	S. aureus (core)
Nasopharyngeal Swab	Blood and Strep select plate, chocolate, chocolate with bacitracin	35°C 5% CO ₂	S. pneumoniae (core) H. influenzae (non-core) N. meningitidis (non-core)
Rectal Swab	Blood and MacConkey	35°C	E. coli (core)

Table 3. Identification of Organisms

Organism	Stain	Identification Tests
S. aureus (core)	Gram stain	Catalase and Tube Coagulase or latex agglutination reagent
S. pneumoniae (core)	Gram stain	Catalase, Optochin disc and/or Desoxycholate reagent, alpha-hemolytic on blood agar
H. influenzae (non-core)	Gram stain	Satelliting growth on blood agar, ALA or other identification tests
N. meningitidis (non-core)	Gram stain	Sugars utilization or other identification kit
S. pyogenes (core)	Gram stain	Catalase, beta-hemolytic on blood agar, and Bacitracin disc or PYR test
E. coli (core)	Gram stain	Indole, oxidase, beta-hemolytic on blood agar, PYR and other identification tests as required

Description of Identification Tests:

We will follow the standard quality control methods already in place at the laboratory. For example, lab staff will perform positive and negative growth controls for all media, and positive controls for all stains and identification tests at a pre-determined schedule.

Catalase Test:

A few drops of 3% hydrogen peroxide are added to colonies removed from agar and smeared onto a clean glass slide, and immediately observed for the release of oxygen or “bubbling.” Bubbling is interpreted as the presence of catalase. Lack of bubbling is a negative test.

Tube Coagulase:

Coagulase plasma is inoculated with an isolated staphylococcal colony and incubated for up to 24 hours at 37°C. Any degree of clot formation is a positive reaction and no clot is a negative reaction.

Latex Agglutination:

A few staphylococcal colonies are mixed with the latex agglutination reagent and observed for agglutination. A positive reaction is agglutination of the latex particles, while no agglutination is a negative reaction.

Optochin Test:

An optochin disc is placed onto a blood agar subcultured plate that has been inoculated with a pure culture of the test organism. Plates are incubated for 24 hours at 35°C in CO₂. If a zone of inhibition of 14 mm or more is formed, then it's *S. pneumoniae*.

Desoxycholate (10%) Test:

A drop of reagent is added to a well-isolated colony on a blood agar plate. Colonies of *S. pneumoniae* will disintegrate after 30 minutes.

Satelliting Growth on Blood Agar:

Colonies resembling *Haemophilus* are subcultured to a non-selective blood agar plate and cross streaked with Coagulase negative *Staphylococcus*. Plates are incubated in CO₂ overnight and examined for satellite growth around *Staphylococcus*.

ALA Test:

Sugars Utilization Tests:

Indole Test:

Oxidase Test:

PYR Test:

13.3.2 Microbiological Resistance Testing for Swabs

Resistance testing will be performed using the Kirby Bauer disc diffusion assay or E-test strips (to determine MIC's).

Quality Control

E. coli ATCC 25922, *S. pneumoniae* ATCC 49619, *H. influenzae* ATCC 49247, *S. aureus* ATCC 25923 and 29213 are used for quality control testing of antibiotic discs and E-test strips.

Kirby Bauer Assay

A suspension of the isolate is prepared and turbidity adjusted until it reaches the 0.5 McFarland standard. The suspension is used to inoculate the appropriate susceptibility agar plate for confluent growth. The plate is allowed to dry. Antimicrobial disks are placed on the agar plates with sterile forceps or tweezers; disks may not be moved once they have touched the plates. After the disks are placed on the plate, the plates are inverted and incubated at 35°C for 16 to 18 hours. After incubation, the diameter of the zones of complete inhibition (including the diameter of the disk) (Figure 2) are measured and recorded in millimeters. The measurements can be made with a ruler or sliding caliper on the undersurface of the plate without opening the lid. The zones of growth inhibition will be compared with the zone-size interpretative table and recorded as

susceptible, intermediate, or resistant to each drug tested according to CLSI guidelines (see Appendix).

Figure 2. Results of the disk diffusion assay. This *Shigella* isolate is resistant to trimethoprim-sulfamethoxazole and is growing up to the disk (SXT), the zone of which is recorded as 6 mm.

E-test strips.

In addition, azithromycin Minimum Inhibitory Concentrations (MIC) are determined using E-test strips. A suspension of the isolate is prepared and turbidity adjusted until it reaches the 0.5 McFarland standard. The suspension is used to inoculate the appropriate susceptibility agar plate for confluent growth. The plate is allowed to dry. E-test strips are placed on the agar plates with sterile forceps or tweezers; strips may not be moved once they have touched the plates. After the strips are placed on the plate, the plates are inverted and incubated at 35°C for 20 to 24 hours. The MIC is read where the ellipse intersects the MIC scale on the strip. The MIC will be compared with the interpretative table according to CLSI guidelines (see Appendix).

Table 4. Antibiotics Testing Guidelines

Specimen	Organism	Antibiotics Tested
Nasal	S. aureus	Azithromycin, cefoxitin
Nasopharyngeal	S. pneumoniae H. influenzae N. meningitidis	Azithromycin, clindamycin, penicillin (Note: S. pneumoniae - 1 ug oxacillin used to predict penicillin resistance for Kirby Bauer)
Stool	E. coli	Azithromycin, ampicillin, co-trimoxazole

Materials Required for Susceptibility Testing:

- MH w/ 5% sheep blood plates
- MHA plates
- MH broth or sterile 0.85% saline
- Sterile cotton-tipped swabs
- 0.5 MacFarland Standard
- Blood and chocolate plates
- Caliper for reading zones
- Forceps
- Light source
- Vortex
- 35°C ambient air and 35°C CO₂ incubator

13.3.3 Nucleic Acid Based Resistance Testing for Stool Specimens

Stool specimens not cultured will undergo nucleic acid based resistance testing. DNA from the stool samples will be extracted using some type of DNA isolation kit (i.e. Norgen Stool DNA Isolation Kit) and the appropriate corresponding protocol.⁴⁹ PCR and gel electrophoresis will then be performed with specific primers to detect genes associated with *E. coli* and antibiotic resistance (specifically macrolide resistance).

Extracting DNA from Stool Procedure

1. Lysate Preparation

- a. Mix the sample well to make sure that the stool/preservative mixture is homogenous. Carefully remove the lid from the collection tube and aliquot 200 μ L of the stool/preservative liquid and add it to a Bead Tube provided with the kit (it may be easier to use a pipet tip that has been cut to make the opening wider or to use a large orifice pipet tip).
- b. Add **Lysis Solution** to the Bead Tube, so that the final volume is 1 ml (for our purposes, add 800 μ L of Lysis Solution). Vortex and centrifuge briefly.
- c. Add 100 μ L of **Lysis Additive** and vortex briefly.
- d. Secure the Bead Tube horizontally on a flat-bed vortex pad with tape, or secure the tube in any commercially available bead beater equipment (e.g. Scientific Industries' Disruptor GenieTM). Vortex for 3 minute at maximum speed.
- e. Centrifuge the tube for 2 minutes at **14000 \times g (~14,000 RPM)**.
- f. Transfer up to 600 μ L of supernatant to a DNAase-free microcentrifuge tube (not provided).
- g. Add 200 μ L of **Binding Solution**, mix by inverting the tube a few times, and incubate for 10 minutes on ice.
- h. Spin the lysate for 2 minutes to pellet any cell debris.
- i. Using a pipet, transfer up to 700 μ L of supernatant (avoid contacting the pellet with the pipet tip) into a 2 ml DNAase-free microcentrifuge tube (not provided).
- j. Add an equal volume of 70% ethanol (provided by the user) to the lysate collected above (100 μ L of ethanol is added to every 100 μ L of lysate). Vortex to mix.

2. Binding to Column

- a. Assemble a spin column with one of the provided collection tubes.
- b. Apply 600 μ L of the clarified lysate with ethanol onto the column and centrifuge for 1 minute at 14000 \times g (~14,000 RPM). Discard the flow through and reassemble the spin column with the collection tube.
Note: Ensure the entire lysate volume has passed through into the collection tube by inspecting the column. If the entire lysate volume has not passed, spin for an additional minute.
- c. Repeat step 2b with the remaining volume of lysate mixture.

3. Column Wash

- a. Apply 500 μ L of **Wash Solution I** to the column and centrifuge for 1 minute.
Note: Ensure the entire wash solution has passed through into the collection tube by inspecting the column. If the entire wash volume has not passed, spin for an additional minute.
- b. Discard the flow through and reassemble the spin column with its collection tube.
- c. Apply 500 μ L of **Wash Solution II** to the column and centrifuge for 1 minute.
- d. Discard the flow through and reassemble the spin column with its collection tube.
- e. Repeat 3c and 3d.
- f. Spin the column for 2 minutes in order to thoroughly dry the resin. Discard the collection tube.

4. DNA Elution

- a. Place the column into a fresh 1.7 mL Elution tube provided with the kit.
- b. Add 50 μ L of **Elution Buffer** to the column.
- c. Centrifuge for 2 minutes at 200 \times g (~2,000 RPM), followed by a 1 minute spin at 14,000 \times g (~14,000 RPM). Note the volume eluted from the column. If the entire volume has not been eluted, spin the column at 14,000 \times g (~14,000 RPM) for 1 additional minute.
- d. (Optional): An additional elution may be performed if desired by repeating steps 4b and 4c using 50 μ L of Elution Buffer. The total yield can be improved by an additional 20-30% when this second elution is performed.

5. Storage of DNA

The purified genomic DNA can be stored at 2-8°C for a few days. For longer term storage, -20°C is recommended.

Amplifying Gene Regions

We will use DNA extracted from stool specimens and published primers to perform PCR reactions for the genes of interest⁵⁰⁻⁵²

Purpose	Genes
Detecting E. coli	malK (encodes for malB promoter) ⁵³ *This gene will detect for both E. coli and Shigella since the two are closely related and are difficult to discriminate from one another.
Detecting Antibiotic Resistance	mph (A, B) erm (A, B, C) mef (A) ere (A, B) msr (A)

13.4 Methods for *Chlamydia trachomatis*

13.4.1 Description of Abbott RealTime Assay

Swabs will be processed with the Abbott RealTime assay for *C. trachomatis*, using the automated Abbott m2000 System. The RealTime assay targets the cryptic plasmid of *C. trachomatis*. The assay has been shown to be highly sensitive and specific for the diagnosis of sexually transmitted *C. trachomatis*, with sensitivities exceeding that of the nucleic acid amplification test used in most recent trachoma studies (Roche AMPLICOR).^{54,55}

13.4.2 Processing of Samples for PCR

Samples are handled as per Abbott RealTime sample processing protocol, with the following modifications:

1. Samples are boiled for 10 minutes at 100°C. Boiling of samples is an accepted treatment method to remove substances that may be inhibitory to the PCR amplification process
2. Samples are pooled.

13.4.3 Procedure for Masking Samples

In order to mask the location origin, the control status, and the clinical exam grading of the conjunctival samples collected in the field, the Database Manager will assign an identification number different from the random number assigned to each child. The PCR results will be recorded according to this laboratory identification number, thus masking the lab until all the samples have been

processed. The Database Manager will then link the lab ID number to the random sample number to reveal the test results by village.

13.4.4 Procedure for Pooling Samples

We will increase the efficiency of chlamydial testing by combining swabs from the same age stratum and same community into pools of 5 random swabs for processing. An internal control will be run with each pool to rule out the possibility of PCR inhibitors. Any inhibitory pools will be re-tested, and if still inhibitory, the swabs will be individually re-tested. If PCR from any pool is equivocal, then all swabs from the pool will be tested individually. While samples will necessarily be diluted in this process, this is not thought to affect the sensitivity of the test.⁵⁶ We will unpool all positive pools in the 0-5 year age stratum and estimate the community prevalence of chlamydial infection as the proportion of positive swabs. We will estimate the community prevalence of infection in the 6-9 and ≥ 10 year age strata using maximum likelihood estimation, similar to our previous trials: the number of individual swabs with the maximum likelihood of having resulted in the observed pooled results will be chosen as the estimate for that village.^{57,58}

In order to pool the conjunctival samples in the lab, the microbiology lab staff will assign a new pool ID number for every sample, and samples will be stored at -80°C freezer until PCR testing (if not processed that day).

13.4.5 Quality Control

1. A *C. trachomatis*(+) control and a *C. trachomatis*(-) control (targeting 136 base pairs of a pumpkin gene) is included in each test run of the Abbott RealTime assay.
2. To test the effect of sample processing, a known positive sample is processed and tested in each test run. (This control is helpful when testing large numbers of negative samples.)
3. An internal control intended to identify specimens that contain polymerase inhibitor is run routinely on each sample. The internal control helps identify false negative results.

13.4.6 Quantification

For every 0-5 year old who tests positive for chlamydia, we will also run PCR for the beta actin gene on the same sample, in order to normalize the quantity of chlamydial DNA to the amount of the specimen. Quantitative results from the Abbott system are given in terms of a decision cycle (DC) number. We will generate a ratio of the DC number of the chlamydial DNA to the DC number of the beta actin gene and use the resulting ratio as the chlamydial load.

Chapter 14: Study Medication

Children aged 1-60 months on the current census will be offered weight- or height-based, directly observed, oral suspension (azithromycin or placebo) every 6 months for 2 years (as performed in trachoma programs) at each study site. In addition to being at least 1 month of age, children should weigh at least 3.8 kg to be eligible for treatment. This ensures that mistakenly aged or premature infants won't be treated. These infants will be eligible for treatment at the subsequent distribution, approximately 6 months later. The mortality application will not provide a dose for children weighing <3.8 kg.

We will monitor adverse events following mass treatments as described in the adverse events section. The treatment and monitoring schedule for all study arms is shown in Table 1.

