5.2.2. Non-core Elements

The designation “non-core” element means that study sites may choose if they wish to perform the study activity. If the study sites perform the study activity, the methodology will be performed according to this protocol so that the 3 sites may be more easily compared. Sites may choose to perform several non-core morbidity assessments at the 0, 12, and 24 month visits:

- Nasal swabs for macrolide resistance in *Staphylococcus aureus*
- Conjunctival swabs for *Chlamydia trachomatis*
- Conjunctival examination and photography to assess for trachoma
- Anthropometric assessments
- Nasopharyngeal swab collection at local health posts to compare macrolide resistance in the community with that in the health post

In addition, there are several non-core activities that occur outside the annual morbidity/resistance assessment:

- Additional study visit during the first malaria season to collect blood samples for malaria and anemia testing
- Clinic-based case finding for childhood illnesses at all health clinics in the study area

Costs

We anticipate recording the cost of distributions in a random subset of 12 villages at the 6 or 12 and 24 month visits.

Details of the non-core elements for each study site can be found in the Appendices.

Chapter 6: Census

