#### Study B (years two and three of mortality contingency study)

1. Sample size considerations are the same as in Study A (year 1).
  - a. Assuming communities of size 668 with approximately 17% in the target age range, an effect size of 20%, 10% loss to follow-up per year, 2% mortality per year, and a CV of 0.51, 312 communities per arm provides approximately 87% power (see MORDOR Phase I SAP for details).
  - b. Updating based on data from Phase I (Niger), we find the following. Assuming the observed CV of 0.34, a death rate of 2% per year results in approximately 80% power to detect a 17% effect. A death rate of 2.5% per year (and a CV of 0.34) result in approximately 80% power to detect a 15.5% effect size.
2. The primary prespecified analysis will contrast the rerandomized placebo arm with the rerandomized azithromycin arm. This will be conducted with negative binomial regression, using a two-sided  $\alpha$  of 0.05 and a permutation test by randomization arm.
3. Supplementary analyses will control for prior history (original randomization arm).
4. Longitudinal analysis for communities who always received azithromycin will be reported.
5. We will compare all four groups for the last year of data (two histories by two final treatments).

6. Additional analyses by the same age groups as before and by phase will be reported.
7. Models of timing, seasonality, and geography will be reported as secondary analysis.

Morbidity Study. Analysis of morbidity communities will follow the exact template as Stage I. Primary prespecified analyses will be two-sided, at an alpha of 0.05. However, the morbidity communities are still receiving placebo. Note that we will report the full follow-up at 48 months separately from the Stage 1 primary analyses. We will also look for secular effects longitudinally over the four years of the full study, as well as phases 5-8 separately.

1. Anthropometry: we will examine height and weight longitudinally, and WFH Z score secondarily. Please see the Stage 1 SAP for details.
2. Other analyses will include drug resistance and malaria, as in Stage 1.
3. Note that we do not do nares or conjunctiva swabs, conjunctival photos, or any swabs on 7-12 year olds in the contingency study.

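### Chlamydial load is defined as a quotient of PCR cycle numbers, which corrects only incompletely for the amount of specimen

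*Protocol*

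**What the plan says.** Protocol 13.4.6 sets out the quantification in four steps.

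- Who is tested: "For every 0-5 year old who tests positive for chlamydia, we will also run PCR for the beta actin gene on the same sample".
- Why: "in order to normalize the quantity of chlamydial DNA to the amount of the specimen".
- Scale of the result: "Quantitative results from the Abbott system are given in terms of a decision cycle (DC) number".
- Definition of load: "We will generate a ratio of the DC number of the chlamydial DNA to the DC number of the beta actin gene", with the instruction to "use the resulting ratio as the chlamydial load".

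The section gives no definition of DC, no direction, no standard curve and no conversion from cycles to copies. Conjunctival swabbing for chlamydia is one of the optional elements in Protocol 5.2.2: "Sites may choose to perform several non-core morbidity assessments at the 0, 12, and 24 month visits". In the contingency study, the SAP says under its Study B morbidity notes that "we do not do nares or conjunctiva swabs, conjunctival photos" are done. The supplied SAP contains no analysis of chlamydial load.

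**The concern.** The section states a purpose and then a formula, and the two do not match. Normalising one quantity of DNA to another means dividing quantities. A cycle number is ordinarily a logarithm of quantity, and division of quantities becomes subtraction of logarithms. Dividing the logarithms leaves part of the specimen effect in the result.

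What is at stake is the meaning of the load value. Two children with the same amount of chlamydia per unit of specimen could receive different loads because one swab picked up more material, and two children with different relative loads could receive the same value. Protocol 5.2.2 wants sites that take up a non-core element to use the common method so that the three sites can be compared. A measure that carries swab yield with it weakens that comparison.

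**Working it through.** The documents give no cycle values and no sample size or power for load, so there is no planned figure to reproduce. All cycle values below are illustrative.

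**Assumptions, none of them in the documents.** DC is linear in the log of template; both targets amplify equally; amplification is 2-fold per cycle unless stated otherwise. Because DC is undefined, two readings are tried: (A) a threshold cycle, lower with more DNA; (B) a cutoff minus the cycle, higher with more DNA, with an illustrative cutoff of 40.

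**Algebra.** Let c and a be the DC numbers for chlamydia and actin. Diluting one specimen F-fold leaves the true chlamydia-to-actin ratio unchanged and shifts both numbers by s = log2(F): up under A, down under B.

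- Difference: (c ± s) − (a ± s) = c − a, unchanged.
- Quotient: (c ± s)/(a ± s), unchanged only if c = a.
- Apparent change in load, in cycles at fixed actin a: s(c − a)/(a + s) under A, s(c − a)/(a − s) under B. The apparent fold change is 2 to that power.

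**Main example, reading A, 8-fold less specimen (s = 3).** 30/24 = 1.250 becomes 33/27 = 1.222. The remainder is 3 × 6/27 = 0.667 cycles, and 2^0.667 = 1.59-fold. With no correction, chlamydia DC would move by 3 cycles, an 8-fold apparent fall. The quotient replaces that with a 1.59-fold apparent rise. The difference is 6 cycles before and after.

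**Other assumed values, 32-fold dilution (s = 5).**

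| Reading | Start | After dilution | Remainder in cycles | Apparent load change |
|---|---|---|---|---|
| A | 30/25 = 1.200 | 35/30 = 1.167 | 5 × 5/30 = 0.833 | 1.78-fold |
| A | 35/25 = 1.400 | 40/30 = 1.333 | 5 × 10/30 = 1.667 | 3.17-fold |
| A | 28/32 = 0.875 | 33/37 = 0.892 | 5 × (−4)/37 = −0.541 | 0.69-fold |
| A | 25/25 = 1.000 | 30/30 = 1.000 | 0 | none |
| B | 10/15 = 0.667 | 5/10 = 0.500 | 5 × (−5)/10 = −2.5 | 0.18-fold |

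The uncorrected comparator is 1/32 = 0.03-fold. Under reading B, pairs that end near the cutoff behave worse. A start of 5/15 becomes 0/10, a remainder of 5 × (−10)/10 = −5 cycles, which is no correction at all. A start of 12/8 becomes 7/3, a remainder of 5 × 4/3 = 6.667 cycles, or about 102-fold.

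**Efficiency.** With 1.9-fold amplification per cycle, the 32-fold results for 30/25 and 35/25 under A are 1.77-fold and 3.13-fold, nearly the same.

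**Equal quotients, different loads (reading A).** 24/20, 30/25 and 36/30 all equal 1.2. The differences are 4, 5 and 6 cycles, so the relative loads are 2^−4 = 0.0625, 2^−5 = 0.0313 and 2^−6 = 0.0156, a 4-fold span.

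**Direction.** Raise chlamydia 8-fold with actin fixed. Under A the quotient goes from 30/25 = 1.20 to 27/25 = 1.08; under B from 10/15 = 0.667 to 13/15 = 0.867.

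**The case against.** The best case for leaving the text alone has four parts.

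- **The quotient does much of the work.** In the main example the specimen effect shrinks from 3 cycles to 0.667. This stands: the quotient does correct, but incompletely, and how well depends on the cycle values.
- **DC is undefined here, and the definition may be elsewhere.** Protocol 5.2.2 sends details of non-core elements to site appendices, and the SAP refers to a Stage 1 SAP; neither is supplied. This stands as a limit on what can be claimed. A definition of DC alone would not rescue the quotient if DC is on a log scale, because the remainder appears under both readings. A conversion to copies before division would.
- **A subtraction rule has assumptions of its own.** It needs the sign of DC and comparable efficiency for the two targets, and the protocol does not say on which platform beta actin is run. This stands and shapes the fix.
- **Little depends on the number.** Protocol 1.2 does not name load in any objective. The prevalence estimate in 13.4.4 uses positive and negative results, and Protocol Chapter 2 says the study areas have little or no trachoma. This stands.

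A reader might go further and infer that the load value runs backwards, so that a higher value means less infection. That follows if DC is a threshold cycle, but no section gives the direction, and under the other reading the quotient rises with load. A reader might also infer that a planned comparison of arms or visits is compromised, or that load data already exist and are wrong. The supplied documents contain no such comparison and do not say that any site has run the beta actin PCR.

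**Conclusion.** The point holds as a definitional error of low materiality. Followed as written, Protocol 13.4.6 yields a load that does not fully achieve the normalisation the same section gives as its purpose. This rests on DC being linear in log template and on a change in specimen amount shifting both DC numbers equally. It does not depend on which way DC runs.

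The size cannot be fixed from the documents. It ranges from nothing, when the two DC numbers are equal, through 1.59-fold for the 8-fold example, to roughly 0.18-fold to 3.2-fold across the tabulated 32-fold dilutions, with larger distortions possible near a cutoff under reading B. Whether a higher value means more or less chlamydia cannot be determined from the text, which is itself a gap.

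The consequence is confined to sites that choose this element and to their chlamydia-positive children aged 0-5.

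**What to change.** In Protocol 13.4.6:

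1. State what DC is and whether it rises or falls with more DNA.
2. Replace the quotient by one of two definitions. Either use the difference of the two DC numbers on the log2 scale (or 2 to that difference), with the sign matched to the stated direction and the amplification efficiencies of both targets given; or convert each target to copies through its own standard curve and divide the copies. The second is safer if the two efficiencies differ.

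The difference needs only the two DC values already planned, so it costs one changed formula and, for any results that exist, a recalculation, provided both values are kept. The standard-curve option also needs calibration data for both targets. If a site appendix or the Stage 1 SAP already defines DC or a conversion, 13.4.6 should refer to it and be brought into line.
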